1.0 General Information

***Please enter the full title of your protocol:**

Comparison of Non-Surgical Treatment Options for Chronic Exertional Compartment Syndrome (CECS)

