This study will be the first of its kind to utilize blinding and a control while analyzing BoNT-A injections for CECS in the military health system. It will also be the first to judge whether formal gait retraining is required for the successful non-operative treatment of CECS or if BoNT-A injections is sufficient as a stand-alone treatment. The information gained from this study has the potential to revolutionize the treatment of CECS and provide guidance to physicians caring for these patients all over the world.

9.3

Objectives/Specific Aims/Research Questions:

Describe the purpose and objective(s) of the study, specific aims, and/or research questions /hypotheses

The long-term objective of this project is to simultaneously assess the effectiveness of non-surgical treatments, botulinumtoxin A (BoNT-A) injections and supervised gait retraining (SGR), in terms of pain control and ability to return to full duty among adult active duty service members suffering from lower extremity Chronic Exertional Compartment Syndrome (CECS), specifically of the anterior and/or lateral compartments.^{1,2,3}

This study will determine if successful supervised gait retraining is required for the successful non-operative treatment of anterior and/or lateral CECS or if BoNT-A injections is sufficient as a standalone treatment. Furthermore, this study will determine if BoNT-A injections plus supervised gait retraining is better.

Study Treatment Groups:

- Group 1 - Home Based Gait Retraining (HBGR) and Normal Saline (placebo)
- Group 2 - Supervised Gait Retraining (SGR) and Normal Saline (placebo)
- Group 3 - BoNT-A + HBGR
- Group 4 - BoNT-A + SGR

Objective 1: Assess and compare the treatment efficacy of the below study treatment groups.

Hypothesis 1: BoNT-A injections will prove effective as a non-surgical treatment option for CECS.

Process for Hypothesis 1: Evaluate functional improvements in Group 3 as compared to Group 1 via the subjective and objective data variables described in protocol sections 10.1 & 10.2.

Hypothesis 2: Supervised Gait Retraining will prove effective as a non-surgical treatment option for CECS.

Process for Hypothesis 2: Evaluate functional improvements in Group 2 as compared to Group 1 via the subjective and objective data variables described in protocol sections 10.1 & 10.2.

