Hypothesis 3: The use of both BoNT-A injections and supervised gait retraining will be more effective than either treatment alone. In adult active duty service members with CECS, the use of both BoNT-A injections and supervised gait retraining returns service members to full duty, including being able to complete their service-specific military physical tests, sooner and for sustained longer periods than SGR or BoNT-A injections alone.

Process for Hypothesis 3: Evaluate functional improvements in Group 4 as compared to Groups 2 & 3 via the subjective and objective data variables described in protocol sections 10.1 & 10.2. Assess the ability of all study groups to complete a 2-mile run and to compete their required service-specific physical fitness testing within the established standards at 8 weeks, 3 months, 6 months, and 12 months post-study injection.

9.4 Study Design:

Describe study design in one to two sentences (e.g., prospective, use of existing records/data /specimens, observational, cross-sectional, interventional, randomized, placebo-controlled, cohort, etc.). Specify the phase – Phase I, II, III, or IV – for FDA-regulated investigational drug research

Multi-site, single-blinded randomized placebo-controlled study

9.5 Target Population:

Describe the population to whom the study findings will be generalized

Adult military beneficiaries diagnosed with Chronic Exertional Compartment Syndrome (CECS)

9.6 Benefit to the DoD:

State how this study will impact or be of benefit to the Department of Defense

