The Informed Consent Form for this research study states that de-identified research data will be shared with the MIRROR/USU and maintained indefinitely for possible use in future research. By consenting for this research study, participants agree to allow us to maintain their de-identified research data indefinitely for possible use in future research.

Data Withdrawal:

Because there will be no way to link an individual's identity to their specific research data, participants will not be able to withdraw their de-identified research data from storage.

Is this a data repository?

☒ Yes ☐ No

If Yes, provide the name of the Repository

USU OCIO REDCap

Who will have access to the Repository?

MIRROR core team, investigators, study team members, as applicable.

Access to the de-identified research data will be governed strictly on an individual-by-individual basis within the secure electronic data capture and management system. Individual data access as well as privileges will be clearly delegated, audited, and monitored by MIRROR/USU.

What data type will be stored in the Repository?

- ☐ Protected Health Information
- ☐ Limited Data Set
- ☒ De-identified Data

11.0

Statistical/Data Analysis Plan

11.1 Data Analysis Plan and Statistical Considerations:

List the statistical methods to be used to address the primary and secondary objectives, specific aims, and/or research hypotheses. Explain how missing data and outliers will be handled in the analysis. The analysis plan should be consistent with the study objectives. Include any subgroup analyses (e.g., gender or age group). Specify statistical methods and variables for each analysis. Describe how confounding variables will be controlled in the data analysis.

To maximize efficiency of the factorial study design, the clinical effectiveness of each treatment will be measured simultaneously using logistic regression analysis. Specifically, the regression model will include three binary independent variables, one for each treatment group, with group 1 (HBGR + NS) as the reference treatment. In this way, the group 3 coefficient (BoNT-A + HBGR) will correspond to the effect estimate of group 3 vs 1 (specific aim 1), the group 2 coefficient (SGR + NS) will correspond to the effect estimate of group 2 vs 1 (specific aim 2), and the group 4 coefficient (BoNT-A + SGR) will correspond to the effect estimate of group 4 vs either 2 or 3 (specific aim 3).

Missing Data and Outliers:

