11.5 Please provide a justification for your sample size

Using a 2x2 factorial design and assuming success rates for passing the US Army 2-mile run test among control (saline/home based gait retraining), botulinumtoxin A (BoNT-A) injection, supervised gait retraining (SGR), and combined therapy (BoNT-A + SGR), respectively, are 15%, 80%, 50%, and 85%, we estimate that enrolling a grand total of at least 60 patients would yield 80% power to detect the effect of BoNT-A, enrolling a grand total of at least 120 patients would yield 80% power to detect the effect of SGR, and enrolling a grand total of at least 380 patients would yield 80% power to demonstrate the benefit of combined therapy (BoNT-A + SGR) vs. either therapy in isolation. If we can obtain complete data on more than 380 participants, then it will strengthen our power. We hope to have a final sample of 480 participants. Assuming roughly 20% attrition and accounting for screen failures, we are requesting to enroll up to 620 participants across all performance sites.

Power was estimated using Monte Carlo simulations assuming uniform randomization among four groups in the 2x2 factorial design, while testing for statistical significance simultaneously among the four groups of control, BoNT-A, SGR, and combined therapy using a generalized linear model. Statistical significance was indicated if the corresponding $p < 0.05$ per generalized linear model.

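### The plan does not pre-specify the one direct comparison of the two active options, BoNT-A (Group 3) against supervised gait retraining (Group 2), although its title and Objective 1 speak of comparing them

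*Combined protocol and SAP*

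**What the plan says.** The title and Objective 1 in section 9.3 are framed as comparisons. Objective 1 reads "Objective 1: Assess and compare the treatment efficacy of the below study treatment groups" and refers to all four arms: Group 1 (HBGR + saline), Group 2 (SGR + saline), Group 3 (BoNT-A + HBGR) and Group 4 (BoNT-A + SGR).

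The three hypotheses then name specific contrasts:

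- Hypothesis 1: "Evaluate functional improvements in Group 3 as compared to Group 1".
- Hypothesis 2: "Evaluate functional improvements in Group 2 as compared to Group 1".
- Hypothesis 3: "Evaluate functional improvements in Group 4 as compared to Groups 2 & 3 via the subjective and objective data variables".

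Section 11.1 analyses these with one logistic model: "the regression model will include three binary independent variables, one for each treatment group, with group 1 (HBGR + NS) as the reference treatment". It assigns the Group 3 coefficient to aim 1, the Group 2 coefficient to aim 2 and the Group 4 coefficient to aim 3.

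Section 11.5 assumes pass rates on the 2-mile run of 15% (control), 80% (BoNT-A), 50% (SGR) and 85% (combined). It gives total sample sizes for the BoNT-A effect (60), the SGR effect (120) and combined therapy against either alone (380). Section 11.2 targets 480 evaluable participants, 120 per group.

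**The concern.** Four groups give six pairwise contrasts. The plan names four as hypotheses: 3 v 1, 2 v 1, 4 v 2 and 4 v 3. A fifth, 4 v 1, is what the Group 4 coefficient actually estimates. The sixth, 3 v 2, is the only one that sets one active option against the other, and it is mentioned nowhere.

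Under the plan's own rates Hypotheses 1 and 2 are both expected to succeed, so the likely headline is that each option beats home training plus saline. Two tests against a shared control do not rank the two treatments. Hypothesis 3 does not rank them either, because it asks whether adding the second treatment helps. A Group 3 v Group 2 result would therefore be post hoc, with endpoint, visit and effect measure chosen after the data are seen. Section 9.6 says high-quality data are lacking for treatment guidelines, and a post hoc result is weaker support for those than a pre-specified one.

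**Working it through.** **Inputs.** Rates 15%, 80%, 50%, 85% (11.5). Uniform allocation, so 380 in total is 95 per group and 480 is 120 per group (11.2, 11.5). Significance level 0.05 (11.5). Two-sided testing is assumed, because sidedness is not stated.

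**The plan's own figures.** These were checked by simulating the 11.1 logistic model with Wald tests (200,000 trials per setting).

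- Total 60, 3 v 1: 82% (random allocation) to 85% (fixed). Consistent with the stated 80%.
- Total 120, 2 v 1: 82%. Consistent.
- Total 380, combined v either alone: not reproduced. 4 v 2 has over 99% power, but 4 v 3 (85% v 80%) has about 14%. The nearest variant is the logit interaction, at 75 to 76%.

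The plan gives no figure for 3 v 2.

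**Power for 3 v 2.** Normal approximation with pooled null variance:

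power = Phi{ [d sqrt(n) - 1.96 sqrt(2 p q)] / sqrt(p3 q3 + p2 q2) }, where p is the mean of the two rates.

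- n = 120, 0.80 v 0.50: [0.30 x 10.954 - 1.96 x sqrt(0.455)] / sqrt(0.16 + 0.25) = (3.286 - 1.322) / 0.640 = 3.07, so 99.9%.
- n = 95: (2.924 - 1.322) / 0.640 = 2.50, so 99.4%.

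The simulated b3 - b2 Wald test agrees to within 0.1 point. For 80% power, 39 per group suffice. If 0.05 were split over four contrasts (0.0125 each), power at 120 per group would still be 99.4%.

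**Precision at 120 per group.** The half-width for the risk difference is 1.96 x sqrt(0.41/120) = 0.115, so 30 points with a 95% CI of about 18.5 to 41.5.

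**The same contrast from the planned model.** Expected successes out of 120 are 18, 60, 96 and 102 in Groups 1 to 4.

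- b3 - b2 = 3.121 - 1.735 = 1.386, an odds ratio of 4.0.
- Its variance is Var(b3) + Var(b2) - 2 Cov(b3, b2). The Group 1 terms cancel, leaving 1/96 + 1/24 + 1/60 + 1/60 = 0.0854, so SE = 0.292 and the 95% CI is 2.26 to 7.09.
- The covariance is needed. It equals 1/18 + 1/102 = 0.0654. Omitting it would give a variance of 0.0854 + 2 x 0.0654 = 0.216 and an SE of 0.465.

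**Sensitivity at 120 per group, SGR held at 50%.** The alternatives for BoNT-A are assumptions. The 72% and 66% come from the retrospective review of 29 patients in 9.2 and concern different outcomes. The 60% has no source in the documents.

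| BoNT-A rate | Power for 3 v 2 |
|---|---|
| 80% | 99.9% |
| 72% | 94% |
| 66% | 71% |
| 60% | 34% |

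The smallest difference detectable with 80% power is about 18 points.

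**The Group 4 coefficient.** With Group 1 as reference, b4 compares Group 4 with Group 1. At the plan's rates its odds ratio is (85/15) / (15/85) = 32.1. The contrasts Hypothesis 3 needs are b4 - b2, odds ratio (85/15) / (50/50) = 5.67, and b4 - b3, odds ratio (85/15) / (80/20) = 1.42.

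**The case against.** The strongest reply is that the trial's specific question does not need 3 v 2. Section 9.3 says "This study will determine if successful supervised gait retraining is required for the successful non-operative treatment", then asks whether BoNT-A suffices alone and whether the two together are better. Those questions rest mainly on 3 v 1 and 4 v 3. The long-term objective is to assess both treatments simultaneously, not to rank them. In a 2x2 factorial, 3 v 2 changes injection and gait-retraining mode together, so leaving it out is a defensible choice. This stands, and it is why a statement that no head-to-head claim will be made is an acceptable remedy. It does not remove the mismatch with Objective 1, which covers comparison of the groups without restriction.

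A reader might also infer that the trial cannot say which option is better. The documents do not support that: every group has its own model term, all four are randomised concurrently, and the contrast has ample power at the assumed rates. Nor do they pose a question about which option to use first. Section 9.6 says only that data are insufficient for guidelines.

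Finally, 3 v 2 is not alone in lacking a coefficient. The 4 v 2 and 4 v 3 contrasts lack one too. That is correct, and it matters more for a stated hypothesis, so the two corrections belong together.

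**Conclusion.** The point holds as a gap in pre-specification. The title and Objective 1 promise a comparison, and the only direct comparison of the two active options has no hypothesis, analysis sentence or power figure. The planned design and sample size can supply it, with 99.4% to 99.9% power at the plan's rates. Power is sensitive to those rates, falling to 71% if BoNT-A reaches 66% with SGR at 50%, although the interval would still be informative. The figures assume two-sided 0.05, a binary 2-mile-run outcome and complete data on 95 or 120 per group.

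Two limits apply to any such result. It compares packages that differ in both injection and gait-retraining mode, and only the injection is blinded. Section 10.1 also reveals the injection assignment after the 3-month visit and then offers active treatments not yet received to participants who are dissatisfied or cannot run 2 miles without symptoms. A later contrast could therefore compare partly crossed-over groups.

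**What to change.** Preferred change:

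- In 9.3, add under Objective 1 that Group 3 will be compared directly with Group 2 as a named secondary comparison.
- In 11.1, define it as b3 - b2 with its covariance, reported as a risk difference and an odds ratio with 95% CIs. Name the outcome (the 2-mile run, as in 11.5) and one visit no later than the 3-month visit. The plan names no single visit for Hypotheses 1 and 2, so this has to be written out.
- State that it compares treatment packages and that the gait component is open-label.

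Alternative: state that no head-to-head conclusion between BoNT-A and SGR will be drawn, and align Objective 1 with that.

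With either choice, rewrite the aim 3 sentence in 11.1 so that Hypothesis 3 is tested by b4 - b2 and b4 - b3, because the Group 4 coefficient alone estimates Group 4 v Group 1.

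The cost is a few sentences. No new data, visits or participants are needed. As a named secondary comparison it leaves the error rates of Hypotheses 1 to 3 unchanged. The small downside is one more secondary result to report.

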Participants who meet final eligibility criteria (no other concomitant causes of leg pain, confirmed CECS diagnosis of the anterior and/or lateral compartments via intramuscular compartment pressure test and lower limb MRI, ABI between 0.90 and 1.40, and if applicable, negative pregnancy test) will be randomized to a study arm and their intervention dates (i.e. injection and/or supervised gait retraining) will be scheduled. Study injections (both placebo and BoNT-A) must occur within 60 days of randomization and ≥ 2 weeks post-intramuscular compartment pressure test. A computer-generated randomization program prepared by the study biostatistician will be used to assign participants uniformly across all four study arms.

Participants will be assigned to one of four treatment groups:

- Group 1 - Home Based Gait Retraining (HBGR) and Normal Saline (placebo)
- Group 2 - Supervised Gait Retraining (SGR) and Normal Saline (placebo)
- Group 3 - BoNT-A + HBGR
- Group 4 - BoNT-A + SGR

Study Intervention:

BoNT-A Injections:

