In keeping with statistical analysis standards in randomized controlled trials, data will be analyzed using complete-case, intention-to-treat (ITT) analysis—that is, we will analyze all study subjects who received treatment assignment and for whom we obtained sufficient outcome data.

Confounding Variables:

Clinical effectiveness will be studied using a factorial randomized design. Such designs are widely recognized to yield unbiased estimates by removing confounding between treatment and outcome when sufficiently powered.

11.2 Sample Size:

We are requesting to enroll up to 620 participants (155 per treatment group) across all performance sites in order to evaluate a final sample of 480 subjects (120 per treatment group) across all performance sites. Up to 125 of these participants will be enrolled at WRNMMC. Up to 125 of these participants will be enrolled at each of the other performance sites.

11.3 Total number of subjects requested (including records and specimens):

620

11.4 If you are recruiting by study arm, please identify the arms of the study and how many subjects will be enrolled in each arm

Across all performance sites, up to 620 participants will be uniformly randomized across the four treatment groups: Up to 155 participants in Group 1 - Home Based Gait Retraining (HBGR) and Normal Saline (placebo), up to 155 participants in Group 2 - Supervised Gait Retraining (SGR) and Normal Saline (placebo), up to 155 participants in Group 3 - BoNT-A + HBGR, and up to 155 participants in Group 4 - BoNT-A + SGR.

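### Chance imbalance between sites is handled neither in the allocation, described only as uniform over four arms, nor in the analysis model, which has no site term

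*Combined protocol and SAP*

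**What the plan says.** Section 9.4 describes a "Multi-site, single-blinded randomized placebo-controlled study". The Randomization paragraph of section 10.1 gives the whole allocation method: "A computer-generated randomization program prepared by the study biostatistician" "will be used to assign participants uniformly across all four study arms". Section 11.4 repeats that "up to 620 participants will be uniformly randomized across the four treatment groups", with up to 155 in each, and the power simulation in section 11.5 assumes the same. Block size, stratification, minimisation, concealment and a rule for enforcing the 155 are not mentioned.

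Section 11.2 sets the totals ("We are requesting to enroll up to 620 participants (155 per treatment group) across all performance sites") and the site limit ("Up to 125 of these participants will be enrolled at each of the other performance sites", with the same limit for the lead site).

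The model in section 11.1 contains one indicator for each of Groups 2, 3 and 4, with Group 1 as reference, and nothing else. On confounding, section 11.1 relies on the factorial randomised design alone.

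**The concern.** Site could plausibly affect outcome here. Supervised gait retraining is delivered by local therapists in group sessions, injections are given by local providers, and the exertion used to confirm the diagnosis may differ between participants. A multi-site trial usually meets this by stratifying the list by site, by putting site in the model, or both. This plan states neither.

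At stake is the precision of every between-arm comparison, and the reader's ability to judge how allocation was generated and concealed. The second matters because only participants are described as blinded and research staff prepare the syringes.

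**Working it through.** **Inputs from the documents.** Maximum 620, 155 per arm; evaluable target 480, 120 per arm; at most 125 per site (section 11.2). About 20% attrition plus an unstated number of screen failures (section 11.5).

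**Inputs assumed.** Five equal sites; between-site SD of 0.25, 0.5 and 1.0 on the logit scale. The documents give no site variation, so a range is shown.

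**1. The plan's totals.** 4 × 155 = 620 and 4 × 120 = 480. 480/(1 − 0.20) = 600, which leaves 620 − 600 = 20 for screen failures. 620/125 = 4.96, so at least five recruiting sites. The totals reproduce.

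**2. Unequal arm totals alone.** Under simple randomisation of 620 the SD of an arm size is √(620 × 0.25 × 0.75) = 10.8. By simulation this raises the variance of a pairwise comparison by about 0.5% at 620 and 0.8% at 380. This part is negligible.

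**3. Imbalance within sites.** At a site of 125 (31.25 expected per arm), simple randomisation gives a single arm a 95% range of 22 to 41, and the largest and smallest arms differ by 11.5 on average. Blocks of 4, or of 4 and 8 mixed, cut that difference to at most 1 or 2.

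**4. Cost in variance.** The sampling SE of a two-arm difference with 155 per arm and 80% success is √(2 × 0.80 × 0.20/155) = 4.54 percentage points. The simulated SD that chance site imbalance adds, and the implied extra variance (added SD/SE)², are:

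| Site SD (logit) | Added SD, points | Extra variance |
|---|---|---|
| 0.25 | 0.41 | (0.41/4.54)² = 0.8% |
| 0.5 | 0.83 | (0.83/4.54)² = 3.3% |
| 1.0 | 1.66 | (1.66/4.54)² = 13% |

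A first-order formula agrees: extra variance ≈ p(1 − p) × SD² × (K − 1)/K. With p = 0.80, K = 5 and SD = 1.0 it gives 0.16 × 1 × 0.8 = 12.8%. Separate simulations comparing unadjusted simple allocation with site-stratified allocation gave about 0–4% at SD 0.25, 3–5% at 0.5 and 11–19% at 1.0, with Monte Carlo error of about 1–1.5%.

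**5. What a site term recovers.** At SD 1.0, simple allocation with site adjustment brought the variance ratio against stratified allocation from about 1.09–1.19 down to about 0.98–1.06.

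**6. The 155 per arm.** Probability that some arm exceeds 155 under simple randomisation, by number randomised:

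| Randomised | Probability |
|---|---|
| 620 | above 99.9% |
| 600 | 90% |
| 580 | 58% |
| 560 | 26% |

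At 620 the mean largest arm is 168, or 13 over. With blocks of 4 and 8 within site and all 620 randomised, some arm still exceeds 155 in about 75% of runs (five sites of 124) to 94% (four of 125 and one of 120), because sites close on incomplete blocks, but only by 1 to 4. With 600 randomised, no blocked run exceeded 155.

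**The case against.** The strongest reply is that equal-ratio wording does not mean simple randomisation. A blocked list, or one permuted list of 620 with exactly 155 per arm, fits the text equally well. That stands: the documents show an unspecified method, not a poor one. It does not supply the missing site term, and nothing in the text says that the list takes account of site.

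Simple randomisation is also unbiased, the precision loss rests on an assumed site SD, and most of it comes from the unadjusted model rather than from the allocation. All of this stands, and it is why the site term comes first in the fix.

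Blocking has its own cost. If unblinded staff know earlier assignments at their site and guess the least-used arm, they are right about 49% of the time with site blocks of 4 and 8, against 25% under simple randomisation. This stands and should be stated in the protocol.

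Three stronger readings are tempting, and the documents support none of them:

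- *The cap is bound to fail and late assignments will be predictable.* The figure above 99.9% needs simple randomisation and all 620 randomised. Section 11.5 appears to count screen failures within the 620. No rule for closing full arms is stated.
- *Site-stratified blocks would hold 155 exactly.* They do so only if sites close on complete blocks or fewer than 620 are randomised.
- *Sites will be badly unbalanced.* At a site of 40, the largest arm is at least twice the smallest with probability 48%. No site sizes are given in the text, five sites reaching 620 would average 124, and at 125 the probability is 4%.

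**Conclusion.** The point holds as a gap in specification with a modest cost in precision. Neither the described allocation nor the stated model deals with site in a trial that needs at least five. There is no bias. The extra variance of the unadjusted contrast is near zero at a site SD of 0.25 and reaches about 19% at 1.0. That range rests on the assumed site SD, about five equal sites and simple allocation; if the program already stratifies by site, the loss from imbalance is largely absent and only the description and the model need changing. The change is worth making because it costs so little, not because the trial's conclusions are threatened.

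**What to change.** 1. **Section 11.1:** add site as a factor in the logistic model. This recovers most of the loss whatever allocation was used. The cost is a few degrees of freedom, and the odds ratio becomes conditional on site, which should be stated.
2. **Section 10.1:** specify central, concealed allocation, stratified by site, in permuted blocks of randomly varying size not disclosed to site staff. State that blocks remain partly predictable to unblinded staff who track earlier assignments. The cost is a different list from the same biostatistician, with no burden on participants. If enrolment has begun, report the method actually used and still make change 1.
3. **Sections 11.2 and 11.4:** describe 155 per arm as an approximate target, since incomplete last blocks can exceed it by 1 to 4 if all 620 are randomised.
4. **Sections 11.4 and 11.5:** reconcile the 620. Section 11.4 has up to 620 randomised. Section 11.5 reaches 620 enrolled by "Assuming roughly 20% attrition and accounting for screen failures", while section 10.1 places formal screening after consent and before randomisation. State how many are consented and how many randomised.
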